5 AIMS AND OBJECTIVES

5.1 AIMS

This trial aims to answer the following questions -

Does the use of serum markers of liver fibrosis:

- a) permit earlier detection of liver cirrhosis in patients with Chronic Liver Disease (CLD) to allow earlier interventions?
- b) affect the process of care, through a) increased use of beta-blockers/band ligation of varices to prevent haemorrhage/HCC; b) increased use of endoscopy and ultrasound/AFP's to detect HCC at a surgically curable stage; and c) effective early treatment to normalise Liver Function Tests (LFT's) in patients with Hepatitis B and Hepatitis C.
- c) result in patient benefit through improved survival and reduced liver-related morbidity and mortality?
- d) improve the cost-effectiveness of the management of end-stage liver disease?

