17.2 SECONDARY ENDPOINTS

- Time from diagnosis of cirrhosis (by ELF or clinical means) to incidence of first severe complication

* Milan criteria: One lesion less than 5cm, up to 3 lesions smaller than 3cm, no extrahepatic manifestations, no vascular invasion.

- Time from randomisation to diagnosis of cirrhosis by ELF or clinical means (to allow instigation of prophylaxis and screening)
- Process outcomes, namely:
 - treatment with beta-blockers/band ligation (BB/BL) of varices
 - use of endoscopy and ultrasound/AFP tests
 - treatment to normalise LFTs in patients with Hepatitis B and Hepatitis C.
- Detection and timing of complications following cirrhosis, including:
 - Detection of small varices
 - Detection of large varices
 - Incidence of treatable hepatocellular cancer (HCC)
- All causes of mortality
- Specific liver-related morbidity
- Economic evaluation of the ELF test in the early detection of cirrhosis and as such in the initiation of measures to reduce the incidence of severe complications following cirrhosis.
- Quality of Life (QoL)
- Proportion of non-randomised patients (ELF < 8.4) who go on to develop cirrhosis (diagnosed by clinical means) within the follow-up period.

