19.2 STATISTICAL ANALYSIS POPULATIONS

All analyses will be conducted on the intention-to-treat (ITT) population and carried out at a 2-sided 5% level of significance. The ITT population is defined as all patients randomised to treatment regardless of non-compliance, loss to follow-up, or death.

The secondary endpoint analysis, incidence of cirrhosis in non-randomised patients, will be conducted on follow-up data from those patients who registered and consented to the trial, but who were not randomised due to having an ELF score of < 8.4 (see section 6.3).

Attempts will be made to retrieve missing data via a thorough data cleaning process.

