19.2.2 Secondary endpoint analysis

Incidence and timing of severe complications of cirrhosis from the date of diagnosis of cirrhosis (in clinic, date of clinic visit or blood sample) will be analysed using Cox regression analysis, adjusting for the minimisation factors (see section 12.2), and will be used to compare the differences between the control and ELF arm. Overall survival curves will be calculated using the Kaplan-Meier method, hazard ratios and corresponding 95% confidence intervals will be presented.

Timing to diagnosis of cirrhosis will be calculated from date of randomisation to the date the patient is diagnosed as having cirrhosis (in clinic) either by, in the ELF arm, having an ELF score ≥ 9.5 or in the control arm, via standard methods. Cox regression analysis, adjusting for the minimisation factors (see section 12.2), will be used to compare the differences between the survival curves, which will be calculated using the Kaplan-Meier method. Hazard ratios and corresponding 95% confidence intervals will be presented.

Detection and timing of complications of cirrhosis will be calculated from the date of diagnosis of cirrhosis, to the detection of the first event. An 'event' in this instance encompasses small and large varices, treatable HCC and inoperable HCC. Cox regression analysis, adjusting for the minimisation factors, will be used to compare the differences between the survival curves. Overall survival curves will be calculated using the Kaplan-Meier method, hazard ratios and corresponding 95% confidence intervals will be presented.

Details of all causes of mortality will be collected and documented, specifically including the number of deaths and whether or not they are suspected to be related to any treatments/trial procedures. All liver-related mortalities will be summarised separately.

Details of the economic evaluation of the ELF test are given in Section 16.

For Quality of Life (QoL), we will look at the difference in expected quality-adjusted survival to final follow-up using the Cox proportional hazards model. We will examine the impact of missing data using a Multiple Imputation method.

The proportion of non-randomised patients (where ELF < 8.4 indicating minimal/mild liver fibrosis) who go on to develop cirrhosis during the follow-up period will be summarised in order to assess false-negative rates (see section 6.3).

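### The complications-detected analysis pools treatable and inoperable HCC with small and large varices in one first event, timed from a post-randomisation diagnosis, so a shift in HCC stage would not show

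*Protocol*

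**What the plan says.** Protocol section 19.2.2 states the time scale and the stopping rule together: "Detection and timing of complications of cirrhosis will be calculated from the date of diagnosis of cirrhosis, to the detection of the first event". It then defines the event as one that "in this instance encompasses small and large varices, treatable HCC and inoperable HCC". The arms are compared by Cox regression adjusted for the minimisation factors, and "Overall survival curves will be calculated using the Kaplan-Meier method, hazard ratios and corresponding 95% confidence intervals will be presented". Under section 19.2 all analyses are "carried out at a 2-sided 5% level of significance" and use the intention-to-treat population. No direction of benefit is given for this event, and no analysis by component is described.

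Other sections treat the components as different things:

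- Section 17.2 lists detection of small varices, detection of large varices and incidence of treatable HCC as three items. Inoperable HCC is not among them.
- Section 5.1 names as an aim "increased use of endoscopy and ultrasound/AFP's to detect HCC at a surgically curable stage", and objective (b) in section 5.2 is in the same spirit.
- Section 17.1 makes HCC beyond the Milan criteria a severe complication and says that HCC within those criteria is not an endpoint because it is treatable. Section 19.2.1 calls the primary-endpoint component unresectable HCC.

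**The concern.** Treatable HCC is what earlier diagnosis of cirrhosis is supposed to find, and HCC beyond Milan is what it is supposed to prevent. Once both stop the same clock, a Cox model cannot tell one from the other. A hazard ratio away from 1 could come from either, and a pure change of stage need not move it at all.

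Two further features add to this. Under the first-event rule, a patient in whom small varices are detected first leaves the analysis, and any later HCC, of either stage, is not counted. And because the clock starts at diagnosis of cirrhosis, only diagnosed patients enter, and the two arms reach diagnosis by different routes. What is at stake is the comparison of the stage at which complications are found, one of several strands of objective (b).

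**Working it through.** The protocol gives no event count, effect size or power for this analysis, so there is no figure to reproduce. The check has three parts.

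**1. Effect of pooling.** For a first event made of competing exponential hazards, the pooled hazard ratio is the average of the component hazard ratios, weighted by each component's share of the control-arm hazard:

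HR_pooled = v × HR_v + t × HR_t + u × HR_u, with v + t + u = 1,

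where v is varices, t treatable HCC and u inoperable HCC.

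Suppose ELF moves 40% of inoperable HCC to treatable and changes nothing else. The 40% is borrowed from the reduction hypothesised in section 18.1. The total detection rate is assumed unchanged. Then HR_pooled = v + (t + 0.4u) + 0.6u = 1, whatever the shares. With f the treatable share of control-arm HCC (not given; assumed 0.3 to 0.7), the forward shift has HR_t = 1 + 0.4(1 − f)/f and HR_u = 0.6. A reverse shift of the same number of cases has HR_t = 1 − 0.4(1 − f)/f and HR_u = 1.4.

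| f | Forward: treatable / inoperable | Reverse: treatable / inoperable | Pooled, both |
|---|---|---|---|
| 0.3 | 1.93 / 0.60 | 0.07 / 1.40 | 1.00 |
| 0.5 | 1.40 / 0.60 | 0.60 / 1.40 | 1.00 |
| 0.7 | 1.17 / 0.60 | 0.83 / 1.40 | 1.00 |

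A gain and a loss are equally invisible. A pooled hazard ratio above 1 is no easier to read. Section 4.2 gives yearly incidences of about 8% for portal hypertension and 5% for HCC. If the first stands in for varices (an assumption), HCC is 5/13 = 0.385 of the total and, at f = 0.5, t = u = 0.192. Half as much again of treatable HCC alone gives 0.615 + 0.192 × 1.5 + 0.192 = 1.10. Half as much again of inoperable HCC alone gives 0.615 + 0.192 + 0.192 × 1.5 = 1.10. The first is a success and the second a failure.

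**2. The first-event rule.** Section 13.1.1 schedules an OGD within 3 months of diagnosis unless one was done in the previous 18 months. Varices present at diagnosis will therefore often be detected first, and those patients contribute nothing to the HCC comparison afterwards.

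**3. The time origin.** The revised projection in section 18.1 has 700 patients randomised, so 350 per arm at 1:1.

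- ELF arm: 40% diagnosed initially plus 10% during follow-up = 50%, or 0.50 × 350 = 175.
- Control arm: under 10%, so fewer than 0.10 × 350 = 35.

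The projection for the 1000-patient design in the same section, on a longer horizon, is less extreme: 216/500 = 43% against 139/500 = 28%. There, about 46 of the 139 control diagnoses (33%) come only when a severe complication occurs. Under either projection the diagnosed groups differ in size and in how they were selected, and the control patients who are never diagnosed drop out. This does not fit the intention-to-treat population that section 19.2 prescribes for all analyses. Adjusting for the minimisation factors does not account for the clinical findings that prompted a control diagnosis.

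**The case against.** The strongest defence has four parts.

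*Direction is less ambiguous than it seems.* A reader might put large varices with inoperable HCC as failures and conclude that the pooled hazard ratio has no direction whatever. The protocol does not support that. Section 13.1.1 makes moderate or large varices the trigger for primary prophylaxis. Section 18.1 bases its power on identifying large varices and predicts beta-blockers or banding in 5% of the ELF arm against 1% of control. More varices found is the expected route to benefit; the variceal failure event is haemorrhage, which is in the primary endpoint. If only inoperable HCC is opposed, its share is at most 5/13 (same proxy as above). With HR 0.6 for it and 1.5 for everything else, the pooled value is at least 0.615 × 1.5 + 0.385 × 0.6 = 1.15; with 1.25 for the rest, at least 1.00. In those scenarios it does not fall on both sides of 1. This stands as a limit on the claim, but it leaves the HCC stage shift hidden.

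*Objective (b) is served elsewhere.* A reader might infer that it cannot be answered at all. That is too broad: the process outcomes, time to diagnosis of cirrhosis and the primary endpoint all bear on it.

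*The components are already named, and the SAP may separate them.* Section 17.2 does list them, its list is introduced as non-exhaustive, and section 19 defers detail to the SAP. But section 19.2.2 does not leave the event open. It states a pooled one, and that wording needs correcting whatever the SAP adds.

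*Counting from randomisation has its own bias.* This is true. Table 4 does not require OGD or ultrasound before diagnosis, whereas section 14.3.1 schedules them after it. More diagnoses in the ELF arm mean more looking. The bias should be disclosed; it does not justify keeping the pooled event.

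**Conclusion.** The point holds for HCC and for the time origin. As written, the analysis counts an intended success and a primary-endpoint failure as one event, discards whatever follows the first detection, and does not match the separate items in section 17.2. A shift of HCC from inoperable to treatable leaves the pooled hazard ratio at 1.00 if the overall detection rate is unchanged; that result does not depend on the assumed shares. The component hazard ratios shown do depend on the assumed 40% shift and on f. They also take inoperable in section 19.2.2 to mean beyond Milan, as sections 17.1 and 19.2.1 suggest.

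The comparison from diagnosis is not between randomised groups: about 175 against fewer than 35 patients on the protocol's own revised projection. No conclusion is drawn about which direction favours ELF for varices of either size. The weakness concerns one secondary analysis and touches neither the primary endpoint nor any stated power figure, but it should be corrected.

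**What to change.** In section 19.2.2, replace the pooled event with four separate analyses: small varices, large varices, treatable HCC, and HCC beyond the Milan criteria. Use that last term consistently in place of inoperable and unresectable, and add it to the list in section 17.2. Analyse each by randomised arm, in all randomised patients, from the date of randomisation.

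State beforehand that more treatable HCC and less HCC beyond Milan favour ELF. State no direction of benefit for varices. Report OGD and ultrasound/AFP uptake by arm next to these results, so that the reader can judge how far detection follows surveillance. Keep any analysis from diagnosis of cirrhosis as description only, without a test between arms.

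The cost is a wording change in the protocol and, where needed, the SAP; the imaging, endoscopy and complication data are already recorded. The price is fewer events and wider intervals for each component, and detection from randomisation will still partly reflect the additional surveillance that a diagnosis sets in train.

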6.1 REGISTRATION

**PLEASE NOTE THAT THE REGISTRATION LINE IS DUE TO CLOSE
28/02/2013**

**PATIENTS MUST NOT BE APPROACHED FOR TRIAL ENTRY AFTER
THIS DATE.**

**IF YOU HAVE APPROACHED PATIENTS PRIOR TO 28/02/2013 WHO ARE
UNABLE TO CONSENT UNTIL AFTER THIS DATE, PLEASE CONTACT
CTRU TO DISCUSS.**

Patients suspected of being at high risk for CLD will be considered for eligibility for registration and invited to provide written, informed consent. If they consent, they will be registered and will provide a serum sample for an ELF test. Patient data will also be collected and recorded (see section 14.1). The ELF test will be analysed and the result of the ELF test will be made available to the investigator normally within 1 week.

Samples can only be used to determine eligibility for randomisation if they have been kept at room temperature for no longer than 2 days between being taken and arriving at iQUR. If shipping delays are anticipated (eg at a weekend), store the serum sample in the fridge and ship when delivery within 2 days is possible. Further guidance related to this can be found in the Sample Processing SSOP. If a sample has been kept at room temperature for

more than 2 days from the time it was taken, then a repeat sample will be required.

Only patients with an ELF score of ≥ 8.4 (denoting at least moderate fibrosis, Table 1) will be eligible for randomisation. Results will be fed back to the investigator as <8.4 not eligible for randomisation or ≥ 8.4 and eligible for randomisation.

At this stage patients will also be invited to participate in the optional translational research biobank research. For this research, a single additional serum sample is required. Whilst patients will consent to the biobank research at the registration visit, this sample will be taken at the randomisation visit i.e. not at the registration visit (please see section 12.5).

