6.2 RANDOMISATION

**PLEASE NOTE THAT THE RANDOMISATION LINE IS DUE TO CLOSE
30/04/2013**

**RANDOMISATIONS MUST BE PERFORMED BY THIS DATE. IF THIS IS
NOT POSSIBLE, PLEASE DISCUSS SPECIFIC CASES WITH CTRU.**

The randomisation visit should occur as soon as possible following receipt of the test results from the registration visit and preferably within 6 weeks of the registration visit, but up to 12 weeks is permissible. However, if there is likely to be a delay in excess of 6 weeks please contact the CTRU to discuss.

If more than 12 weeks has passed since registration, a repeat ELF test should be taken to ensure that the patient remains eligible for the trial, and has not progressed to cirrhosis. The patient should then be randomised within the timeframes above for the closure of the randomisation line.

Patients with a registration ELF score of ≥ 8.4 will return to clinic for their randomisation visit when it will be explained that their ELF test has demonstrated they are above the threshold for randomisation. They will be asked to confirm whether or not they are still happy to continue participating in the trial and willing to be randomised. Patients will also be assessed to ensure their liver disease has not progressed to clinically evident cirrhosis in the interval from their registration visit.

Should the patient be judged at this visit to still be pre-cirrhotic, proceed with 24 hour telephone randomisation whilst patient is in clinic completing the Randomisation Visit Patient Questionnaires.

Should the patient be judged to have developed clinical signs/symptoms of cirrhosis they are no longer regarded as eligible for the trial. Please DO NOT proceed with randomisation. The patient should begin management for cirrhosis according to local practice.

Patients with an ELF score of <8.4 will also have no further study participation and will resume normal care. However, all patients who consent to the trial (whether randomised or not) will be flagged with the NHS Information Centre for longer term morbidity and mortality data from the Medical Research Information Service and Hospital Episode Statistics (please see section 6.3) These patients may be contacted by telephone to explain and discuss the reasons why they are ineligible for the study. A written explanation may also be provided (please see Investigator Site File for 'ELUCIDATE Letter for Ineligible Patients').

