12.3 SCREENING FOR CIRRHOSIS WITH ELF

Subjects in the intervention arm will have their ELF score measured every 6 months. If the ELF score is ≥ 9.5 the patient will be deemed to have cirrhosis. These patients should be contacted as soon as possible and recalled in to clinic to commence cirrhosis management. (Please see section 13)

Patients in the ELF arm will also be screened for cirrhosis using standard clinical means. If the patient is deemed to be cirrhotic on clinical criteria (by examination, on the basis of laboratory tests (other than ELF) or through imaging), the patient will have been deemed to have cirrhosis and cirrhosis management will commence.

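### The proportion of ELF <8.4 registrants who develop cirrhosis is labelled as assessing false-negative rates, but it is 1 − NPV of the entry threshold, taken from routine records

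*Protocol*

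**What the plan says.** Section 17.2 lists the secondary endpoint "Proportion of non-randomised patients (ELF < 8.4) who go on to develop cirrhosis (diagnosed by clinical means) within the follow-up period". Section 19.2 restricts its analysis to registered, consenting patients "but who were not randomised due to having an ELF score of < 8.4". Section 19.2.2 gives the purpose: patients "who go on to develop cirrhosis during the follow-up period will be summarised in order to assess false-negative rates".

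Two different ELF thresholds are in use. The entry gate is in section 6.1: "Only patients with an ELF score of ≥ 8.4 (denoting at least moderate fibrosis, Table 1) will be eligible for randomisation". The diagnostic rule is in section 12.3: "If the ELF score is ≥ 9.5 the patient will be deemed to have cirrhosis".

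On follow-up, section 6.2 says that patients below 8.4 "will also have no further study participation and will resume normal care". Sections 6.2, 6.3 and 11 have them flagged with routine NHS data sources. Randomised patients not yet diagnosed with cirrhosis are examined and have blood tests every 6 months (section 14.2, Table 4).

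**The concern.** A false-negative rate is 1 − sensitivity: of the patients who have cirrhosis, the share the test calls negative. The planned proportion runs the other way: of the patients the test calls negative, the share who turn out to have cirrhosis. Since most patients below 8.4 are expected to have mild disease or none, that proportion can be small whatever the sensitivity is.

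Two further features separate it from a miss rate of the test as the trial uses it. The threshold is 8.4, whereas ELF calls cirrhosis at 9.5. Patients at 8.4 to 9.49 who are clinically cirrhotic are also negative under the diagnostic rule but fall outside this analysis. And the cirrhosis status of patients below 8.4 comes from routine records, although section 4.4.1 notes that cirrhotic patients often have no symptoms.

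Objective 5.2(a) is to evaluate how well ELF performs in early detection of cirrhosis. A reader given a figure of, say, 2% as a false-negative rate would naturally take sensitivity to be 98%, which the figure cannot support.

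**Working it through.** The protocol states no false-negative rate, so there is no such figure to reproduce. The check shows how far the two quantities can differ on the protocol's own planning numbers.

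**Inputs**
- Registered for 1000 randomised: 2160 (section 18.2), so 2160 − 1000 = 1160 with ELF <8.4.
- Original plan, control arm (section 18.1): 46 diagnosed through severe complications, 62 diagnosed clinically with ELF >9.49, and 10% of 315 = 31.5 from ELF 8.4–9.49. The sum is 139.5, which agrees with the stated 139 of 500, or 278 per 1000.
- Revised plan (section 18.1): clinical cirrhosis in under 10% of control patients by July 2014. Taking 10% gives 100 per 1000.
- Cirrhosis rate p below 8.4: not given in the protocol. Assumed to be 1%, 2% or 5%.

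**Formulas**
- Planned proportion = (cirrhosis with ELF <8.4) / 1160 = p.
- Share of recorded cirrhosis lying below the gate = x / (x + c), where x = 1160p and c is recorded cirrhosis above the gate per 1000 randomised. This treats all 1000 as if monitored like controls.

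**Results**

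| Assumed p (what the plan reports) | x | c = 278 | c = 100 |
|---|---|---|---|
| 1% | 11.6 | 11.6/289.6 = 4.0% | 11.6/111.6 = 10.4% |
| 2% | 23.2 | 23.2/301.2 = 7.7% | 23.2/123.2 = 18.8% |
| 5% | 58.0 | 58/336 = 17.3% | 58/158 = 36.7% |

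Scaling to about 700 randomised leaves the ratios as they are: 1160 × 0.7 = 812 below the gate, and 812 × 2% = 16.2, so 16.2/(16.2 + 70) = 18.8%.

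**Recording.** If routine records capture only half of the cases below 8.4 (an assumption), a true 2% is observed as 1%. With c = 278, the share below the gate then falls from 7.7% to 11.6/289.6 = 4.0%.

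**Opposite direction.** The endpoint counts patients who go on to develop cirrhosis. Disease that arises after the baseline sample was not there for the test to find, so counting it as a miss overstates the error of the baseline test. The protocol gives no figures from which to net these two effects.

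**The case against.** The fairest defence is that only the statement of purpose is wrong. Section 17.2 calls the endpoint a proportion, and section 19.2 calls it an incidence in non-randomised patients. Nothing says it will be reported as 1 − sensitivity. Asking how many patients turned away at 8.4 later develop cirrhosis is a sensible check of that gate, and it is a single-group description with no comparison between differently followed groups. This stands: the quantity is worth having, but its label is not right.

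A reader might go further and infer that ELF is bound to look far more sensitive than it is. The documents do not support that. No cirrhosis rate below 8.4 is given, incident disease works in the other direction, and the net bias is not determined.

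A reader might also compute a true miss rate for the 9.5 rule by adding the expected progressors at 8.4–9.49 (10% of 630 = 63). At p = 2% this gives (23.2 + 63)/(23.2 + 278) = 28.6%. That is not a sound estimate. Section 18.1 describes those patients as developing or progressing to cirrhosis, ELF-arm patients are retested every 6 months, and the 278 belongs to the original 1000-patient plan.

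Nor can it be said that the protocol gives no basis for a better measure. Table 5 (code R) requires one ELF test in control-arm patients once clinical cirrhosis is confirmed. The protocol states no analysis of these results, but it defers detail to an analysis plan not examined here.

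**Conclusion.** The point holds as a mislabelled quantity. What sections 17.2, 19.2 and 19.2.2 define is the false omission rate of the 8.4 entry gate over follow-up, as seen in routine records. It does not measure the share of cirrhosis that ELF misses, and it is silent on the 9.5 rule.

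The size is illustrative only. For an assumed 2% below 8.4, the share of recorded cirrhosis below the gate is about 8% or about 19%, depending on which of the protocol's control-arm figures is used. Both values rest on the assumed 2%, on the 2160-to-1000 ratio, and on equal recording on either side of the gate. That last condition is doubtful, because control patients have 6-monthly examinations and blood tests and patients below 8.4 do not.

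This is a descriptive secondary endpoint. The primary endpoint, its power and the comparisons between arms are not touched.

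**What to change.** - In sections 17.2 and 19.2.2, call the quantity the cumulative incidence of recorded cirrhosis in patients with ELF <8.4 (1 − NPV of the entry threshold), and state that it comes from routine data. Remove the reference to false-negative rates.
- Report the miss rate of the 9.5 rule separately: among control-arm patients with confirmed clinical cirrhosis, the proportion whose ELF at diagnosis (Table 5, code R) is below 9.5, and separately the proportion whose baseline ELF is below 9.5, each with a confidence interval. State that it applies only to patients who were above the 8.4 gate at entry.
- If the ELF <8.4 registrants are pooled with the control arm to estimate a miss rate over the whole range, present it as a sensitivity analysis only and state that detection differs between the groups.

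The cost is a wording change and one extra descriptive analysis of data the trial already collects. The limitation is few cases. With about 350 control patients and under 10% clinically cirrhotic by July 2014, there would be at most about 35, and a 95% interval could be as wide as ±1.96 × √(0.25/35) = ±17 percentage points.

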3 FLOW DIAGRAM

*Registration line due to close 28/02/2013

**Randomisation line due to close 30/04/2013

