6.3 FOLLOW-UP

From the date of randomisation, patients will undergo follow-up assessments every 6 months until 30 months post-randomisation, unless they are diagnosed as cirrhotic. Where patients are diagnosed as cirrhotic within 30 months post-randomisation, an initial follow-up assessment will take place at 3 months after diagnosis, and subsequent visits for the purposes of data collection will take place at 6-monthly intervals. . All patients who consent to the trial (whether randomised or not) will be flagged with the NHS Information Centre for longer term morbidity and mortality data from the Medical Research Information Service and Hospital Episode Statistics (see section 11).

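### Cirrhosis in the ELF <8.4 cohort is reported as a proportion over a follow-up period with no start or length for these patients, so it has no time horizon and moves with the data cut

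*Protocol*

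**What the plan says.** Protocol 17.2 lists as a secondary endpoint: "Proportion of non-randomised patients (ELF < 8.4) who go on to develop cirrhosis (diagnosed by clinical means) within the follow-up period". Section 19.2 limits the population to registered, consenting patients who were not randomised because of ELF <8.4, and calls the quantity an incidence: "The secondary endpoint analysis, incidence of cirrhosis in non-randomised patients, will be conducted on follow-up data from those patients who registered and consented". Section 19.2.2 gives the analysis: the proportion "who go on to develop cirrhosis during the follow-up period will be summarised", with the stated aim of judging false negatives. It refers to section 6.3 for the follow-up.

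Section 6.3 gives one length: "patients will undergo follow-up assessments every 6 months until 30 months post-randomisation". For those not randomised it gives only the flagging: "All patients who consent to the trial (whether randomised or not) will be flagged with the NHS Information Centre for longer term morbidity", with no end date. Section 6.2 confirms that patients below 8.4 take no further part in the study beyond flagging. The flow diagram in section 3 gives the end of entry: "Registration line due to close 28/02/2013".

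In the same section 19.2.2, the three timed endpoints (severe complications after diagnosis, time to diagnosis of cirrhosis, and complications after diagnosis) are assigned Kaplan-Meier curves and Cox regression. All-cause mortality, like the ELF <8.4 endpoint, is only counted and summarised.

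**The concern.** A proportion developing an event is interpretable only if everyone is observed for the same known time, or if the estimator allows for unequal observation. Neither is provided for here. The patients enter over about two years, have no scheduled visits, and are observed until whatever date the flagging data are cut. The stated 30 months starts at an event they never reach.

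This is the only listed endpoint devoted to the patients turned away at the 8.4 threshold, and its stated purpose is to judge false negatives. A figure with no horizon cannot be read as a risk at 2 years, 30 months or 5 years. Two analysts could also compute it over different windows and both be following the protocol.

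**Working it through.** **Inputs.**
- Start of entry: about April 2011, from section 19.1 (summer 2013, taken as July, is roughly 27 months after recruitment to version 5.0 began). Any earlier start is not dated, so March 2010 is used as an assumed sensitivity value.
- End of entry: end of February 2013 (section 3), giving an entry period a = 23 months.
- Data cuts: July 2014 (section 19.1). A late cut five years on is taken as July 2019, or January 2020 if counted from the end of the grant.
- Hazard: the protocol gives none for ELF <8.4. A constant hazard of 10% per 42 months is assumed, with 2% to 20% as the range.

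**Formula.** With uniform entry over a months, minimum follow-up f and hazard λ, the expected simple proportion is P = 1 − [exp(−λf) − exp(−λ(f+a))]/(aλ).

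**Check against the protocol's own figure.** Section 18.1 uses this type of model for 185 control patients: 22% at 36 months, 24 months of recruitment, 30 months of follow-up. λ = −ln(0.78)/36 = 0.006902, f = 30, a = 24, giving 185 × P = 46.4 events. The protocol states 46.4.

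**Follow-up in the ELF <8.4 cohort.**
- July 2014: 16 to 39 months, mean 27.5.
- July 2019: 76 to 99 months, mean 87.5.

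**Open-ended window, 10% per 42 months.** λ = −ln(0.9)/42 = 0.0025086 and aλ = 0.057697.
- July 2014: 1 − (0.960657 − 0.906799)/0.057697 = 6.65%.
- July 2019: 1 − (0.826420 − 0.780087)/0.057697 = 19.7%.

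**True risk at fixed horizons, 1 − exp(−λh), the same at every cut.**

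| Horizon (months) | 12 | 24 | 30 | 36 | 60 |
|---|---|---|---|---|---|
| Risk | 3.0% | 5.8% | 7.2% | 8.6% | 14.0% |

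The July 2014 figure lies above the 12- and 24-month risks and below those at 30 months and later. It equals the risk at about 27 months. The July 2019 figure exceeds the risk at every horizon below about 87 months.

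**Error for the 30-month risk (7.25%) at July 2014.**
- All events counted: 6.65/7.25 = 0.92, so 8% too low. If follow-up is rounded to 17–39 months and the 30-month risk is taken as 3%, the proportion is 2.80% and the shortfall 7%.
- Only events within 30 months of registration counted: 6.25/7.25 = 0.86, so 14% too low. Only 9/23 = 39% of patients have reached 30 months.
- These shortfalls change by less than one percentage point across the hazard range.

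**Change with the cut.**
- Open-ended window, July 2019 against July 2014: 19.7/6.65 = 2.96. The ratio is 2.74 to 3.14 for hazards of 20% down to 2% per 42 months.
- Across both start dates and both late cuts the ratio is 2.4 to 3.35.
- Window of 30 months from registration: 7.25/6.25 = 1.16. By 2019 everyone has completed the window and the error is gone.

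**Sensitivity to the start date.** If entry began in March 2010 (a = 36), mean follow-up at July 2014 is 34 months and the crossing point moves to about 34 months. The open-ended proportion is then 8.14%, about 12% above the 30-month risk. The 30-month-window version is 6.61%, about 9% below it.

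**The case against.** The strongest case against is that the protocol never says how the proportion is computed. A Kaplan-Meier or cumulative-incidence estimate is also a proportion, section 19.2 uses the word incidence, and section 19 leaves further detail to the SAP, which is not at hand. It is true that a simple count over a denominator is an inference, drawn mainly from the contrast with the timed endpoints in 19.2.2. But the endpoint definition itself, with no origin or length for this cohort, is in section 17.2 of the protocol.

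The effect is also small. On an assumed 3% risk, the July 2014 shortfall is 0.2 to 0.4 percentage points. With about 812 patients (700 × 2160/1000 − 700), the sampling half-width is 1.96 × √(0.03 × 0.97/812) = 1.2 points. That stands, and it limits the importance of the point.

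A reader might infer more than the documents support:
- *That the proportion understates risk at every horizon.* It does not. It overstates risk at horizons shorter than about the mean follow-up.
- *That the reported figure will change three-fold.* That needs an open-ended window and a late re-analysis of this endpoint. Section 19.1 names the late analysis only for time to first severe complication.
- *That early deaths bias it.* A competing-risk cumulative incidence also treats those patients as never developing cirrhosis. The problem is unequal follow-up.
- *That it cannot be compared with the 10% progression assumed for ELF 8.4–9.49 because that figure has a defined period.* Section 18.1 states the 10% over staggered follow-up too.
- *That this is the only information on the cohort.* Section 11 says flagging supplies endpoint data for all registered patients.

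**Conclusion.** The point holds in a limited form. Sections 17.2 and 19.2.2 fix a proportion over a period that is undefined for patients who are never randomised. Taken as a simple proportion, it corresponds to no stated horizon: at July 2014 it matches the risk at about 27 months, overstating risk before that and understating it after.

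For the 30-month risk it is about 7–14% too low in relative terms. This assumes a constant hazard and uniform entry from about April 2011; the size barely depends on the hazard level. An earlier start would shift the crossing point and, with an open-ended window, could reverse the sign at 30 months. The rise by a cut five years later is roughly 2.4- to 3.4-fold with an open-ended window and re-analysis, and about 1.16-fold with a 30-month window. That the text permits such different answers is the defect. No between-arm comparison is affected.

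**What to change.** In 17.2 and 19.2.2, replace the proportion by the cumulative incidence of clinically diagnosed cirrhosis, with registration as time origin, at stated horizons: for example 24 or 30 months, plus a later one if the endpoint is re-analysed after longer follow-up. Censor at the data cut, treat death without cirrhosis as a competing event, and give 95% confidence intervals.

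The analysis needs only the dates of registration, diagnosis and death, and no extra visits. The cost is a small amount of analysis and a wording change in the protocol and SAP.
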